### **5.3.5.7 Abnormal Liver Function Tests**

The finding of an elevated ALT or AST ( $>3 \times$  baseline value) in combination with either an elevated total bilirubin ( $>2 \times$  ULN) or clinical jaundice in the absence of cholestasis or other causes of hyperbilirubinemia is considered to be an indicator of severe liver injury (as defined by Hy's Law). Therefore, investigators must report as an adverse event the occurrence of either of the following:

- Treatment-emergent ALT or AST  $>3 \times$  baseline value in combination with total bilirubin  $>2 \times$  ULN (of which  $\geq 35\%$  is direct bilirubin)
- Treatment-emergent ALT or AST  $>3 \times$  baseline value in combination with clinical jaundice

The most appropriate diagnosis or (if a diagnosis cannot be established) the abnormal laboratory values should be recorded on the Adverse Event eCRF (see Section 5.3.5.2) and reported to the Sponsor immediately (i.e., no more than 24 hours after learning of the event), either as a serious adverse event or an adverse event of special interest (see Section 5.4.2).

### **5.3.5.8 Deaths**

All deaths that occur during the protocol-specified adverse event reporting period (see Section 5.3.1), regardless of relationship to study drug, must be recorded on the Adverse Event eCRF and immediately reported to the Sponsor (see Section 5.4.2). This includes death attributed to progression of Multiple Myeloma.

Death should be considered an outcome and not a distinct event. The event or condition that caused or contributed to the fatal outcome should be recorded as the single medical concept on the Adverse Event eCRF. Generally, only one such event should be reported. If the cause of death is unknown and cannot be ascertained at the time of

reporting, "**unexplained death**" should be recorded on the Adverse Event eCRF. If the cause of death later becomes available (e.g., after autopsy), "unexplained death" should be replaced by the established cause of death. The term "**sudden death**" should not be used unless combined with the presumed cause of death (e.g., "sudden cardiac death").

If the death is attributed solely to progression of multiple myeloma, "multiple myeloma progression" should be recorded on the Adverse Event eCRF.

Deaths that occur after the adverse event reporting period should be reported as described in Section 5.6.

#### **5.3.5.9 Preexisting Medical Conditions**

A preexisting medical condition is one that is present at the screening visit for this study. Such conditions should be recorded on the General Medical History and Baseline Conditions eCRF.

A preexisting medical condition should be recorded as an adverse event only if the frequency, severity, or character of the condition worsens during the study. When recording such events on the Adverse Event eCRF, it is important to convey the concept that the preexisting condition has changed by including applicable descriptors (e.g., "more frequent headaches").

#### **5.3.5.10 Lack of Efficacy or Worsening of Multiple Myeloma**

Events that are clearly consistent with the expected pattern of progression of the underlying disease should not be recorded as adverse events. These data will be captured as efficacy assessment data only. In rare cases, the determination of clinical progression will be based on symptomatic deterioration. However, every effort should be made to document progression through use of objective criteria. If there is any uncertainty as to whether an event is due to disease progression, it should be reported as an adverse event.

#### **5.3.5.11 Hospitalization or Prolonged Hospitalization**

Any adverse event that results in hospitalization (i.e., inpatient admission to a hospital) or prolonged hospitalization should be documented and reported as a serious adverse event (per the definition of serious adverse event in Section 5.2.2), except as outlined below.

An event that leads to hospitalization under the following circumstances should not be reported as an adverse event or a serious adverse event:

- Hospitalization for respite care
- Hospitalization solely for coordination of care, including hospice arrangements
- Hospitalization that was necessary because of patient requirement for outpatient care outside of normal outpatient clinic operating hours

- Planned hospitalization required by the protocol (e.g., for study drug administration or insertion of access device for study drug administration)

Patients who are hospitalized to extend the observation period following study drug administration, either at the discretion of the investigator or because the patient experienced an IRR during or following the first dose (see Section 4.3.2.1), should not automatically be considered to have had a serious adverse event. In such cases, the investigator should consider whether the adverse event required hospitalization (regardless of the need for observation) or met seriousness criteria unrelated to hospitalization when determining whether an adverse event is serious.

- Hospitalization for a preexisting condition, provided that all of the following criteria are met:

The hospitalization was planned prior to the study or was scheduled during the study when elective surgery became necessary because of the expected normal progression of the disease

The patient has not experienced an adverse event

- Hospitalization due solely to progression of the underlying cancer

#### **5.3.5.12 Reporting Requirements for Cases of Accidental Overdose or Medication Error**

Accidental overdose and medication error (hereafter collectively referred to as "special situations"), are defined as follows:

- Accidental overdose: accidental administration of a drug in a quantity that is higher than the assigned dose
- Medication error: accidental deviation in the administration of a drug

In some cases, a medication error may be intercepted prior to administration of the drug.

Special situations are not in themselves adverse events, but may result in adverse events. Each adverse event associated with a special situation should be recorded separately on the Adverse Event eCRF. If the associated adverse event fulfills seriousness criteria, the event should be reported to the Sponsor immediately (i.e., no more than 24 hours after learning of the event; see Section 5.4.2). For RO7297089, adverse events associated with special situations should be recorded as described below for each situation:

- Accidental overdose: Enter the adverse event term. Check the "Accidental overdose" and "Medication error" boxes.
- Medication error that does not qualify as an overdose: Enter the adverse event term. Check the "Medication error" box.
- Medication error that qualifies as an overdose: Enter the adverse event term. Check the "Accidental overdose" and "Medication error" boxes.

In addition, all special situations associated with RO7297089, regardless of whether they result in an adverse event, should be recorded on the Adverse Event eCRF as described below:

- Accidental overdose: Enter the drug name and "accidental overdose" as the event term. Check the "Accidental overdose" and "Medication error" boxes.
- Medication error that does not qualify as an overdose: Enter the name of the drug administered and a description of the error (e.g., wrong dose administered, wrong dosing schedule, incorrect route of administration, wrong drug, expired drug administered) as the event term. Check the "Medication error" box.
- Medication error that qualifies as an overdose: Enter the drug name and "accidental overdose" as the event term. Check the "Accidental overdose" and "Medication error" boxes. Enter a description of the error in the additional case details.
- Intercepted medication error: Enter the drug name and "intercepted medication error" as the event term. Check the "Medication error" box. Enter a description of the error in the additional case details.

As an example, an accidental overdose that resulted in a headache would require two entries on the Adverse Event eCRF, one entry to report the accidental overdose and one entry to report the headache. The "Accidental overdose" and "Medication error" boxes would need to be checked for both entries.

#### **5.3.5.13 Safety Biomarker Data**

Adverse event reports will not be derived from safety biomarker data by the Sponsor, and safety biomarker data will not be included in the formal safety analyses for this study. In addition, safety biomarker data will not inform decisions on patient management.

### **5.4 IMMEDIATE REPORTING REQUIREMENTS FROM INVESTIGATOR TO SPONSOR**

Certain events require immediate reporting to allow the Sponsor to take appropriate measures to address potential new risks in a clinical trial. The investigator must report such events to the Sponsor immediately; under no circumstances should reporting take place more than 24 hours after the investigator learns of the event. The following is a list of events that the investigator must report to the Sponsor within 24 hours after learning of the event, regardless of relationship to study drug:

- Serious adverse events (defined in Section 5.2.2; see Section 5.4.2 for details on reporting requirements)
- Adverse events of special interest (defined in Section 5.2.3; see Section 5.4.2 for details on reporting requirements)
- DLTs during the DLT assessment window (defined in Section 5.2.4; see Section 5.4.2 for details on reporting requirements)
- Pregnancies (see Section 5.4.3 for details on reporting requirements)

For serious adverse events and adverse events of special interest, the investigator must report new significant follow-up information to the Sponsor immediately (i.e., no more than 24 hours after becoming aware of the information). New significant information includes the following:

- New signs or symptoms or a change in the diagnosis
- Significant new diagnostic test results
- Change in causality based on new information
- Change in the event's outcome, including recovery
- Additional narrative information on the clinical course of the event

Investigators must also comply with local requirements for reporting serious adverse events to the local health authority and IRB/EC.

#### **5.4.2 Reporting Requirements for Serious Adverse Events, Adverse Events of Special Interest, and Dose-Limiting Toxicities**

##### **5.4.2.1 Events That Occur prior to Study Drug Initiation**

After informed consent has been obtained but prior to initiation of study drug, only serious adverse events caused by a protocol-mandated intervention should be reported. The paper Clinical Trial Serious Adverse Event/Adverse Event of Special Interest Reporting Form provided to investigators should be completed and submitted to the Sponsor or its designee immediately (i.e., no more than 24 hours after learning of the event), either by faxing or by scanning and emailing the form using the fax number or email address provided to investigators.

##### **5.4.2.2 Events That Occur after Study Drug Initiation**

After initiation of study drug, serious adverse events and adverse events of special interest will be reported until 90 days after the final dose of study drug. DLTs will be reported during the DLT assessment window. Investigators should record all case details that can be gathered immediately (i.e., within 24 hours after learning of the event) on the Adverse Event eCRF and submit the report via the electronic data capture (EDC)

system. A report will be generated and sent to Safety Risk Management by the EDC system.

In the event that the EDC system is unavailable, the paper Clinical Trial Serious Adverse Event/Adverse Event of Special Interest Reporting Form provided to investigators should be completed and submitted to the Sponsor or its designee immediately (i.e., no more than 24 hours after learning of the event), either by faxing or by scanning and emailing the form using the fax number or email address provided to investigators. Once the EDC system is available, all information will need to be entered and submitted via the EDC system.

Instructions for reporting serious adverse events that occur > 90 days after the final dose of study treatment are provided in Section 5.6.

### **5.4.3 Reporting Requirements for Pregnancies**

#### **5.4.3.1 Pregnancies in Female Patients**

Female patients of childbearing potential will be instructed to immediately inform the investigator if they become pregnant during the study or within 28 days after the final dose of study drug. A paper Clinical Trial Pregnancy Reporting Form should be completed and submitted to the Sponsor or its designee immediately (i.e., no more than 24 hours after learning of the pregnancy), either by faxing or by scanning and emailing the form using the fax number or email address provided to investigators. Pregnancy should not be recorded on the Adverse Event eCRF. The investigator should discontinue study drug and counsel the patient, discussing the risks of the pregnancy and the possible effects on the fetus. Monitoring of the patient should continue until conclusion of the pregnancy. Any serious adverse events associated with the pregnancy (e.g., an event in the fetus, an event in the mother during or after the pregnancy, or a congenital anomaly/birth defect in the child) should be reported on the Adverse Event eCRF. In addition, the investigator will submit a Clinical Trial Pregnancy Reporting Form when updated information on the course and outcome of the pregnancy becomes available.

#### **5.4.3.2 Pregnancies in Female Partners of Male Patients**

Male patients will be instructed through the Informed Consent Form to immediately inform the investigator if their partner becomes pregnant during the study or within 28 days after the final dose of study drug. A paper Clinical Trial Pregnancy Reporting Form should be completed and submitted to the Sponsor or its designee immediately (i.e., no more than 24 hours after learning of the pregnancy), either by faxing or by scanning and emailing the form using the fax number or email address provided to investigators. Attempts should be made to collect and report details of the course and outcome of any pregnancy in the partner of a male patient exposed to study drug. When permitted by the site, the pregnant partner would need to sign an Authorization for Use and Disclosure of Pregnancy Health Information to allow for follow-up on her pregnancy. If the authorization has been signed, the investigator should submit a Clinical Trial

Pregnancy Reporting Form when updated information on the course and outcome of the pregnancy becomes available. An investigator who is contacted by the male patient or his pregnant partner may provide information on the risks of the pregnancy and the possible effects on the fetus, to support an informed decision in cooperation with the treating physician and/or obstetrician.

#### **5.4.3.3 Abortions**

A spontaneous abortion should be classified as a serious adverse event (as the Sponsor considers abortions to be medically significant), recorded on the Adverse Event eCRF, and reported to the Sponsor immediately (i.e., no more than 24 hours after learning of the event; see Section 5.4.2).

If a therapeutic or elective abortion was performed because of an underlying maternal or embryofetal toxicity, the toxicity should be classified as a serious adverse event, recorded on the Adverse Event eCRF, and reported to the Sponsor immediately (i.e., no more than 24 hours after learning of the event; see Section 5.4.2). A therapeutic or elective abortion performed for reasons other than an underlying maternal or embryofetal toxicity is not considered an adverse event.

All abortions should be reported as pregnancy outcomes on the paper Clinical Trial Pregnancy Reporting Form.

#### **5.4.3.4 Congenital Anomalies/Birth Defects**

Any congenital anomaly/birth defect in a child born to a female patient exposed to study drug or the female partner of a male patient exposed to study drug should be classified as a serious adverse event, recorded on the Adverse Event eCRF, and reported to the Sponsor immediately (i.e., no more than 24 hours after learning of the event; see Section 5.4.2).

### **5.5 FOLLOW-UP OF PATIENTS AFTER ADVERSE EVENTS**

#### **5.5.1 Investigator Follow-Up**

The investigator should follow each adverse event until the event has resolved to baseline grade or better, the event is assessed as stable by the investigator, the patient is lost to follow-up, or the patient withdraws consent. Every effort should be made to follow all serious adverse events considered to be related to study drug or trial-related procedures until a final outcome can be reported.

During the study period, resolution of adverse events (with dates) should be documented on the Adverse Event eCRF and in the patient's medical record to facilitate source data verification.

All pregnancies reported during the study should be followed until pregnancy outcome.

### **5.5.2 Sponsor Follow-Up**

For serious adverse events, adverse events of special interest, and pregnancies, the Sponsor or a designee may follow up by telephone, fax, email, and/or a monitoring visit to obtain additional case details and outcome information (e.g., from hospital discharge summaries, consultant reports, autopsy reports) in order to perform an independent medical assessment of the reported case.

### **5.6 ADVERSE EVENTS THAT OCCUR AFTER THE ADVERSE EVENT REPORTING PERIOD**

After the end of the adverse event reporting period (defined as 90 days after the final dose of study drug), all deaths, regardless of cause, should be reported through use of the Long-Term Survival Follow-Up eCRF.

In addition, if the investigator becomes aware of a serious adverse event that is believed to be related to prior exposure to study drug, the event should be reported through use of the Adverse Event eCRF. However, if the EDC system is not available, the investigator should report these events directly to the Sponsor or its designee, either by faxing or by scanning and emailing the paper Clinical Trial Serious Adverse Event/Adverse Event of Special Interest Reporting Form using the fax number or email address provided to investigators.

### **5.7 EXPEDITED REPORTING TO HEALTH AUTHORITIES, INVESTIGATORS, INSTITUTIONAL REVIEW BOARDS, AND ETHICS COMMITTEES**

The Sponsor will promptly evaluate all serious adverse events and adverse events of special interest against cumulative product experience to identify and expeditiously communicate possible new safety findings to investigators, IRBs, ECs, and applicable health authorities based on applicable legislation.

To determine reporting requirements for single adverse event cases, the Sponsor will assess the expectedness of these events through use of the reference safety information in the document listed below:

Drug	Document
RO7297089	RO7297089 Investigator's Brochure

The Sponsor will compare the severity of each event and the cumulative event frequency reported for the study with the severity and frequency reported in the applicable reference document.

Reporting requirements will also be based on the investigator's assessment of causality and seriousness, with allowance for upgrading by the Sponsor as needed.

## **6. STATISTICAL CONSIDERATIONS AND ANALYSIS PLAN**

No formal hypothesis testing is planned. Descriptive statistics will be used to summarize the safety, tolerability, pharmacokinetics, and clinical activity of RO7297089. Data will be described and summarized as warranted by number of patients in question. Listings will be used in place of tables for small numbers of patients. All analyses will be based on the safety-evaluable population, defined as all patients who receive any amount of study drug.

Continuous variables will be summarized using means, standard deviations, median and ranges; categorical variables will be presented using counts and percentages. All summaries will be presented by dose cohort to which a patient was originally assigned.

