### **3.1.1.2 Dose-Escalation Rules**

The starting dose of RO7297089 will be 60 mg, administered IV weekly for Cohort 1.

Dose escalations will be guided by the mCRM-EWOC model ([Appendix 11](#)). The MTD is defined as the dose that maximizes the probability of a DLT being in the targeted toxicity interval in the range of 20%–35%, subject to the probability of the DLT being in the excessive toxicity interval in the range of 35%–100% being <25%. For each cohort, patients will be followed through a 14-day DLT assessment window. At each dose-escalation step, the dose can be escalated or de-escalated and/or an additional cohort at that same dose level could be enrolled. Refer to Section 3.1.1 for additional information. If MTD is not reached, the RP2D will be determined based on the totality of data including clinical activity, safety, PK, and pharmacodynamics biomarkers. Once the MTD or is RP2D determined, all patients in dose-escalation will be eligible to receive the RP2D, based upon ISC decision.

In addition, different dosing regimens (e.g., every 2 weeks) may be explored in parallel, if warranted, on the basis of the safety and PK profile of RO7297089, with DLT periods specific for each regimen and starting dose not exceeding the weekly MTD. Any evaluation of a different administration schedule will be based on the recommendation of the ISC and reviewed with study investigators. Addition of different dosing regimens will require a protocol amendment. For this new regimen, the mCRM-EWOC model and priors as defined in [Appendix 11](#), as well as the simulations, will be reviewed and possibly modified and the DLT assessment period will be extended to 21 days to ensure that patients have received at least two doses of study drug.

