### **3.1.3 Inpatient Dose Escalation**

To maximize the collection of information at relevant doses and minimize the exposure of patients to sub-optimal doses of RO7297089, inpatient dose escalation may be permitted. Within each assigned dose-escalation cohort, the dose of RO7297089 for an individual patient may be increased to the highest cleared dose level that is tolerated by completed cohorts through *the DLT window*. Patients may be able to undergo inpatient dose escalation after completing at least two cycles at their originally assigned dose level.

Subsequent inpatient dose escalations may occur after at least one cycle of any subsequently higher cleared dose level without any adverse event that meets the definition of a DLT or necessitates post-administration hospitalization (Section 3.1.1.1). Once the MTD is declared and the RP2D is determined, inpatient dose escalation directly to the RP2D is permitted for patients who remain on study and continue to tolerate RO7297089.

*At the discretion of the investigator and in consultation with the Medical Monitor, the RO7297089 administration schedule for the first cycle after inpatient dose escalation may follow any administration schedule previously evaluated in the study.*

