#### **6.4.1            Analyses of Exposure, Adverse Event, Laboratory, and Vital Sign Data**

Safety will be assessed through summaries of exposure to study treatment, adverse events, changes in laboratory test results, and changes in vital signs and ECGs.

Study treatment exposure (such as treatment duration, total dose received, and number of cycles and dose modifications) will be summarized with descriptive statistics.

All verbatim adverse event terms will be mapped to Medical Dictionary for Regulatory Activities (MedDRA) thesaurus terms, and adverse event severity will be graded according to NCI CTCAE v5.0. All adverse events, serious adverse events, adverse events leading to death, adverse events of special interest, and adverse events leading to study treatment discontinuation that occur on or after the first dose of study treatment (i.e., treatment emergent adverse events) will be summarized by mapped term, appropriate thesaurus level, and severity grade. For events of varying severity, the highest grade will be used in the summaries. Deaths and cause of death will be summarized.

Relevant laboratory, vital sign (pulse rate, respiratory rate, blood pressure, and temperature), and ECG data will be displayed by time, with grades identified where appropriate. Additionally, a shift table of selected laboratory tests will be used to summarize the baseline and maximum post-baseline severity grade. Changes in vital signs and ECGs will be summarized.

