## **6.6 ACTIVITY ANALYSES**

Response assessment data and duration of response will be summarized for all patients by cohort.

Objective response is defined as a sCR, CR, VGPR, or PR as determined by investigator assessment using IMWG response criteria. Patients with missing or no response assessments will be classified as non-responders. The objective response rate will be summarized for patients receiving the recommended Phase II dose.

Among patients with an objective response, duration of response will be defined as the time from the initial objective response to the time of disease progression or death. If a patient does not experience disease progression or death before the end of the study, duration of response will be censored at the day of the last tumor assessment. If no tumor assessments were performed after the time of first objective response, duration of response will be censored at the time of first objective response.

OS is defined as the time from the first day of study treatment (Day 1 of Cycle 1) to death. If a patient has not experienced death, OS will be censored at the day of last contact. Preliminary OS data may be tabulated and summarized using time-to-event analyses for patients receiving the RP2D.

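### Adverse events, laboratory grades and responses first seen after a within-patient dose change are tabulated under the originally assigned dose, and no table by actual dose is planned

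*Combined protocol and SAP*

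**What the plan says.** The general rule in Section 6 is: "All summaries will be presented by dose cohort to which a patient was originally assigned". Section 6.6 follows it for activity: "Response assessment data and duration of response will be summarized for all patients by cohort".

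Dose is not fixed within a patient. Section 3.1.3 (headed inpatient escalation, although Appendix 3 uses the word intrapatient) says: "Patients may be able to undergo inpatient dose escalation after completing at least two cycles at their originally assigned dose level". The move may go to the highest cleared level. Section 3.1.1.2 adds that, once the MTD or RP2D is set, "all patients in dose-escalation will be eligible to receive the RP2D, based upon ISC decision". In the other direction, Section 5.1.2.1 allows up to two dose reductions for drug-related toxicity.

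Section 6.4.1 sets how severity is reported. For adverse events: "For events of varying severity, the highest grade will be used in the summaries". For laboratory data, "a shift table of selected laboratory tests will be used to summarize the baseline and maximum post-baseline severity grade". Neither sentence cuts follow-up at a dose change or refers to the dose at onset.

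On the RP2D, Section 6.6 says: "The objective response rate will be summarized for patients receiving the recommended Phase II dose". An optional preliminary OS summary uses the same description of the patients.

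**The concern.** Read together, these rules produce tables in which the row label and the dose can part company. A patient assigned 60 mg who has a Grade 1 event there, and whose grade first worsens to Grade 3 after moving to 180 mg, appears as a Grade 3 patient in the 60 mg cohort. A reader of that table would take it as evidence about 60 mg.

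This matters because Section 2.1 lists the relationship of dose to safety and activity among the endpoints of the primary objective, and by-cohort tables are the natural place to look for it. The protocol itself treats the first higher dose as a fresh risk. Section 4.3.2.1 requires at least a 2-hour infusion and 4 hours of observation, and Table 2 repeats the first-dose vital sign schedule. Yet a reaction on that day would be reported under the dose the patient had left.

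A smaller matter is that Section 6.6 gives no membership rule for patients receiving the RP2D. It does not say how to treat escalation-stage patients moved to that dose later.

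**Working it through.** **1. Can later events reach the DLT and MTD analysis?** Two 14-day cycles are 28 days, so the two-cycle rule in Section 3.1.3 permits escalation no earlier than nominal Day 29. The DLT window ends on Day 14 (Arms A and B) or Day 21 (Arm C: Cycle 1 Day 8 to Cycle 2 Day 7). With the 7-day extension the latest end is Day 28. Post-escalation events therefore fall outside the window that feeds the model. They do fall inside the worst-grade, shift and response tables.

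**2. When could a patient in an original escalation cohort escalate?** The higher dose must already be cleared. Assume the fastest case in Arms A or B: 3 patients, the first two 72 hours apart, 14-day windows and immediate decisions.
- The first cohort doses on Days 1 and 4 and clears at the end of Day 4 + 13 = Day 17.
- The next cohort doses on Days 18 and 21 and clears at the end of Day 21 + 13 = Day 34.
- Appendix 1 places the first higher dose on Day 1 of a cycle, so the first nominal date is Cycle 4 Day 1, which is 3 × 14 + 1 = Day 43.

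Day 29 is reachable only for patients enrolled when a higher dose is already cleared, such as backfill patients.

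**3. Response.** Scheduled SPEP and free light chain samples fall on Cycle 1, 3 and 5 Day 1, that is Days 1, 29 and 57, and are drawn before infusion. A response first seen on Day 29 belongs to the original dose. With escalation on Day 43, one first seen on Day 57 follows 42 days at the original dose and 57 − 43 = 14 days at the higher one. That is mixed exposure, and it is a reason to flag the dose, not to reassign the response.

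**4. Weight of one misfiled patient.** 1/6 = 16.7 points and 1/9 = 11.1 points. In the minimum cohort of 3 it is 33.3 points, but Section 6 may present so small a group as a listing only.

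**5. Dose gap for one step**, from Appendix 11 Table 1 (no DLTs):

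| From (mg) | To (mg) | Ratio |
|---|---|---|
| 60 | 180 | 3.00 |
| 180 | 500 | 2.78 |
| 500 | 1180 | 2.36 |
| 1180 | 1600 | 1.36 |
| 1600 | 1650 | 1.03 |

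**6. The RP2D response rate.** The plan's interval in Section 6.1 reproduces: 0.20 ± 1.645 × √(0.20 × 0.80 / 30) = 7.99% to 32.01%, stated as 8% to 32%. It applies to 30 expansion patients. If k later-escalated patients were pooled in and a fraction r responded, the rate would be (6 + rk)/(30 + k). The documents give neither k nor r. Taking r from 0 to 0.4 as an assumption, k = 5 gives 17.1% to 22.9% and k = 10 gives 15% to 25%. At r = 0.2 the rate stays at 20%.

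**The case against.** The strongest reply is that grouping by assigned dose is legitimate, the study is descriptive with no hypothesis test, and no decision rule depends on these tables. All of that stands, and it is why the assigned-dose tables should remain.

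The plan also has partial safeguards. Section 6.4.1 summarises total dose and dose modifications, and "ECG data will be displayed by time, with grades identified where appropriate", a provision that also covers laboratory and vital sign data. Adverse event timing is an endpoint in Section 6.4. Sections 2.2 and 2.6 relate exposure to safety and activity. Section 6.7 groups immunogenicity by treatment received. The infusion reactions reported in Section 5.1.1.1 occurred in Cycle 1, before any escalation. These provisions help, but none assigns an adverse event, laboratory grade or response to the dose at which it arose.

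On the RP2D set, the reply is largely right. Section 3.1.4 treats expansion patients at the RP2D, Section 6 groups by assignment and Section 6.1 bases precision on n = 30, so the natural reading is patients assigned the RP2D. What is missing is a sentence saying so.

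A reader might infer that the denominator could grow to all 60–80 enrolled patients. Section 3.1.3 does not support that: a direct move to the RP2D is limited to patients still on study and tolerating treatment.

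**Conclusion.** The point holds for the descriptive dose-safety and dose-activity summaries and should be fixed. As written, the plan files some findings under a dose the patient was no longer receiving and offers no table that shows the actual dose.

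A reader might infer that the MTD is biased; step 1 shows that it is not. The expansion interim rules are likewise unaffected. A reader might also infer that low doses will look too toxic or too active. That direction is not established, because events after a dose reduction are filed under a higher dose than the one being given.

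The size rests on how many patients change dose, which the documents do not state. What can be said is 17 points per event in a cohort of 6, and a gap of 1.03- to 3.0-fold for one step. Because Section 3.1.3 permits a move to the highest cleared level, a larger gap is possible. The RP2D wording is a secondary clarification.

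**What to change.** - Keep every assigned-dose table.
- Add supplementary adverse event and laboratory shift tables by actual dose level at onset, with exposure time at each level. Footnote that they are sparse, and that post-escalation data come only from patients who completed at least two cycles, so dose is confounded with time on treatment and tolerance.
- Keep response by assigned dose without censoring at escalation. Flag each response with the actual dose at first documentation and whether that was before or after a dose change.
- In Section 6.6, define the RP2D response rate, and any OS summary, as covering patients originally assigned the RP2D, with expansion patients as the main row to match n = 30. Show patients later escalated to it separately. OS runs from Cycle 1 Day 1, so those patients have by definition survived to the switch.

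The cost is plan wording, some programming and a few thin tables that need cautious reading. Section 4.3.2 already has dose modifications noted on the Study Drug Administration eCRF, and Section 5.3.5.4 captures grade changes. The sponsor should confirm that the date and dose of each escalation are recorded.
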